Development of infectious diseases and vaccine-preventable diseases	All emergency department visits and hospitalizations will be reported as an adverse event. If the subject is hospitalized with lower respiratory tract symptoms of unknown etiology, nasal wash will be obtained for pertussis PCR. If S. pneumoniae is isolated from the blood or a sterile body site (such as cerebrospinal fluid), isolates will be serotyped.
Development of septicemia and opportunistic infections	All events with bacteremia, fungemia, or other opportunistic infections will be reported as an adverse event.

Impaired response to childhood vaccines

Subjects will receive all routine childhood vaccines according to the schedule recommended by the American Academy of Pediatrics (AAP), with the exception of up to a 4-week delay of vaccines that would have been given during the first 4 weeks of the study drug/placebo. Vaccinations will be administered by the subject's primary care provider. At 18 months of age or at the time of liver transplantation (if younger than 18 months of age), the vaccination records of each subject will be obtained from the primary care provider for review. The number and size of doses, dates of administration, and vaccine manufacturer will be recorded. At the age of 18 months, 6-9 ml of blood will be obtained to measure serum antibody titers against individual vaccine antigens. The antibody titers will be measured by the study sites local laboratory. If a subject has received a transplant before the 18th month visit, titers should not be collected. Priority titers to be collected relate to vaccinations for Hepatitis B, Tetanus, and Polio. If serum antibody titers do not achieve protective levels as determined by the local laboratory standard and the investigator, the information will be provided to the primary care provider so that booster/re-immunization of appropriate antigen(s) is given. Absent titers will also be communicated to the primary care provider, who will treat with re-immunization as directed by the AAP guidelines for catch-up immunization.

Development of infectious diseases and vaccine-preventable diseases

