Subjects will be prospectively monitored for the development of infectious diseases and vaccine-preventable diseases. Treatment with corticosteroids often induces a leukocytosis (with or without mild bandemia). This leukocytosis is usually benign and expected to decrease as the dose of corticosteroid decreases. If leukocytosis is associated with any other signs or symptoms that may indicate infection (e.g.: fever, lethargy, poor feeding), the primary care provider will further evaluate and treat as clinically indicated, according to local standard of care.

Parents and primary care providers of all enrolled subjects will be instructed to contact the study coordinator promptly at the time of any infectious acute illness that leads to visit to the primary care provider, to an emergency department, or if the subject requires hospitalization. An Adverse Event Form will be completed within 24 hrs of each report. If a child is hospitalized because of a respiratory tract illness of unknown etiology, microbiology studies will be pursued according to the local standard of care, but an additional nasal aspirate will be obtained for rapid screen for *B. pertussis*. If *S. pneumoniae* is isolated from a sterile body site (e.g.: blood, cerebrospinal fluid) or lower respiratory tract by bronchial lavage, the isolate will be serotyped to determine if it is a vaccine-related strain. These diagnostic studies will be performed, when possible, by the admitting hospital's clinical microbiology laboratory; alternatively, samples may be performed by an outside laboratory, such as Quest Diagnostic Laboratories.

Development of septicemia and opportunistic infections

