Subjects will be monitored for the development of infections or serious opportunistic infections (bacterial, viral, fungal). Evaluation of the subject with a febrile illness will proceed as per the local standard of care and antimicrobials will be initiated accordingly. completed. If the infection is associated with hypotension, acidosis, or tissue necrosis, a Serious Adverse Event Form will be completed. The decision to break the study medication code and institute stress dose replacement with corticosteroid for subjects in the corticosteroid arm of the study will be made by the clinical center PI based on the clinical status of the subject. If a serious opportunistic infection is diagnosed, appropriate antimicrobial therapy will be initiated and a Serious Adverse Event Form will be completed. If the subject is still receiving study drug/placebo, the drug/placebo will be tapered and discontinued according to the protocol outlined in Table 5.

4.P. Research Versus Standard Clinical Care

One important feature of this clinical trial is that subjects will receive standard clinical care at ChiLDREN centers in addition to the care related to enrollment in the trial. As outlined in Table 9, participation in this trial will specifically require: 1) randomization to receive either corticosteroids or placebo, 2) treatment with ranitidine during the duration of study drug/placebo, 3) outpatient visit at 2 weeks after portoenterostomy, 4) serum concentration of electrolytes, glucose, bile acids, and PIVKA-II, 5) developmental assessment, 6) HRQOL inventory, and 7) evaluation of serum antibody titers to vaccines. All other outpatient visits and laboratory studies are routinely performed as part of standard clinical care of infants with biliary atresia, as summarized in Table 9 below.

Table 9. Outline of Care Related to this Clinical Trial Versus Standard Clinical Care

Health Care Item	Collected by*
Medical encounters/visits	
• 2 weeks after portoenterostomy	T
• 1,2,3,6 months after portoenterostomy	DB,CC
• 12,18,24 months after portoenterostomy	DB,CC
Standard diet and nutritional support	DB,CC
Vitamin supplementation	T
Ursodeoxycholic acid	T
Antibiotic prophylaxis for ascending cholangitis	DB,CC
Administration of study drug/placebo	T
Administration of ranitidine	T
Childhood immunizations	CC
Laboratory monitoring	
• Complete blood count	DB,CC
• LFTs, PT/INR	DB,CC
• Serum retinol, RBP, 25OH-Vitamin D	CC,T
• Serum vitamin E, total lipid ratio	CC,T

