In this study, an SAE is defined as any clinical adverse event or abnormal laboratory test value that is associated with events that could threaten a subject's life or functioning,

irrespective of the study arm (corticosteroids or placebo) to which the subject was assigned. The term SAE is not intended as a measure of severity or intensity⁷⁷⁻⁷⁹. Thus, an AE should be considered a SAE if it results in any of the following:

- Death
- Is life-threatening (subject was at risk of death as a result of the event; it does not refer to hypothetical risk of death if the event had been more severe)
- Requires insubject hospitalization or prolongation of an existing hospitalization
- Results in persistent or significant disability/incapacity
- A congenital anomaly/birth defect
- Is medically significant or requires intervention to prevent one or other of the outcomes listed above

7.C. AE and SAE Reporting Plan

An investigator from the DCC will serve as the Medical Safety Officer. He/she will carry a pager so that all SAEs may be reported promptly. The DSMB will review all AEs and SAEs during their regularly scheduled meetings, or on an expedited basis as determined by the NIDDK Program Director or Chair of the DSMB, according to the ChiLDREN policy manual.

All unexpected adverse events (UAEs) are reported to the DCC by completion of the Adverse Events Form by the study site into the secure ChiLDREN website. This triggers an email message to the Medical Safety Officer to check the website for the report; no personal identifying or medical information is contained in the email message.

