- Return to the operating room in less than 30 days for wound management.
- A late complication in wound healing following portoenterostomy, such as, ventral hernia, ascitic leak, etc

Wound healing will be assessed daily in the hospital after portoenterostomy by the clinical team. A formal evaluation by the clinical site PI and study coordinator will occur on the day of discharge and at weeks 2 and 4 after portoenterostomy. Delay in discharge or readmission due to wound healing complications after surgery will be reported as an SAE. Wound infection that requires specific treatment with intravenous antibiotics will also be reported as a SAE. At outpatient study visits, an assessment will be made as to whether there is adequate wound healing. If there is a wound infection requiring surgical intervention in the operating room (i.e. reoperation) or complete wound dehiscence, it will be reported as a SAE. In the event of any SAE, drug or placebo will be tapered and discontinued (Section 4.F3). Care of the subject for impaired wound healing will be done according to local standard of care.

7.D5. Gastrointestinal Bleeding

If hematochezia, melena, hematemesis, or visible blood through nasogastric or gastrostomy tube is reported, an evaluation of gastrointestinal bleeding will be performed (e.g., to rule out anal fissure, infectious colitis, allergic colitis). If the bleeding is not associated with a drop in hematocrit and no further evaluation is indicated, a mild AE will be reported. If the presence of hematemesis, hematochezia or melena is associated with a drop in hematocrit of >5%, a moderate AE will be reported and further evaluation will be considered as clinically indicated; the clinical site PI will have the option to initiate study medication dose reduction (Section 4.F2). If a packed red blood cell transfusion is required and/or endoscopic intervention (such as sclerotherapy) is necessary, this will be reported as a SAE. The presence of a hemoglobin level < 6.5 g/dl or systemic hypotension caused by acute gastrointestinal bleeding will also be reported as a SAE, and the study drug or placebo will be tapered and discontinued (Section 4.F3).

7.D6. Pancreatitis

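### The infection and event-specific reporting rules (4.O3, Table 8, 7.D) do not carry through the hospitalization criterion of the SAE definition in 7.B3, so hospitalized events may be under-classified and SAE counts may vary by site

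*Protocol*

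**What the plan says.** **Definition.** Protocol 7.B3 lists the outcomes that make an adverse event serious. One is "Requires insubject hospitalization or prolongation of an existing hospitalization". The same section states: "The term SAE is not intended as a measure of severity or intensity". Section 7.C requires notification of SAEs, as so defined, within 24 hours. Severity has its own scale in 7.B2, Grades 1 to 5.

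**Infections.** Table 8 in 4.O3 says "All emergency department visits and hospitalizations will be reported as an adverse event" and "All events with bacteremia, fungemia, or other opportunistic infections will be reported as an adverse event". For infectious illness leading to a primary care visit, an emergency visit or a hospital stay, the text of 4.O3 says "An Adverse Event Form will be completed within 24 hrs of each report". A separately named serious-event form appears in the paragraph on septicemia, with two triggers: "If the infection is associated with hypotension, acidosis, or tissue necrosis, a Serious Adverse Event Form will be completed"; and "If a serious opportunistic infection is diagnosed, appropriate antimicrobial therapy will be initiated and a Serious Adverse Event Form will be completed".

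**Other events.** 7.D2, 7.D3, 7.D5 and 7.D6 set out steps from mild and/or moderate AE up to SAE. In 7.D5, for instance, bleeding "associated with a drop in hematocrit of >5%, a moderate AE will be reported", and the SAE steps are transfusion, endoscopic intervention, hemoglobin below 6.5 g/dl or hypotension. In 7.D6, pancreatitis is first a moderate AE; SAE is reached if symptoms persist, need narcotic pain relief or come with listed complications. 7.D4 (wound healing) differs: readmission and delayed discharge are SAEs.

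**The concern.** A site coordinator with a hospitalized infant can look up the event in 4.O3 or 7.D, or apply the criteria in 7.B3, and the two routes can give different answers. The protocol does not rank them.

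This matters because SAE status has several uses. 7.B1 calls for AEs and SAEs to be compared between arms. Section 8 gives the DSMB quarterly summaries split by serious and non-serious status. 7.C ties 24-hour notification and expedited FDA reporting to it. Infection is one of the corticosteroid risks listed in 4.F1, so serious infection is a category the trial most needs to count the same way at all 14 centers.

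**Working it through.** No figure in the protocol is at stake, so the check is to classify the same event under each section.

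| Event (infant admitted in each case) | 7.B3 | Event-specific section, read literally |
|---|---|---|
| Bacteremia; no hypotension, acidosis or tissue necrosis; not opportunistic | SAE (hospitalization) | Table 8 and 4.O3: adverse event; neither serious-form trigger met |
| Pancreatitis, lipase above three times the upper limit, resolving without narcotics or complications | SAE | 7.D6: moderate AE |
| GI bleeding, hematocrit drop above 5%, no transfusion or endoscopic intervention, hemoglobin above 6.5 g/dl, no hypotension | SAE | 7.D5: moderate AE |
| Potassium 2.5 to below 3 mmol/L | SAE | 7.D3: moderate AE |
| Readmission for a wound complication | SAE | 7.D4: SAE |

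The first four rows diverge and the last agrees. In the divergent rows the deciding fact under 7.B3 is the admission, which the event-specific rule does not ask about when it sets the class. The ladders also put SAE where a higher severity grade would stand, although 7.B3 says seriousness is not severity.

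**Direction of the effect.** The trial is double-blind, so for a given type of event the share recorded as non-serious should be similar in both arms. Write it as a capture share s: risks p1 and p2 become s·p1 and s·p2, and the difference shrinks to s·(p2 − p1). Equal risks stay equal, so no false difference is created.

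**Illustration only.** The documents give neither SAE risks nor a capture share; both are assumed here. With n = 70 per arm (5.A.1), two-sided 5%, and p̄ the mean of the two recorded risks:

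power = Φ{ [ |p2 − p1| − 1.96·√(2p̄(1 − p̄)/n) ] / √[ (p1(1 − p1) + p2(1 − p2))/n ] }

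- Assumed 40% vs 60%, s = 1: (0.20 − 1.96 × 0.0845)/0.0828 = 0.415, so power is 66%.
- Same risks, s = 0.5 (20% vs 30%): (0.10 − 1.96 × 0.0732)/0.0727 = −0.60, so power is 27.5%.

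| Assumed true risks | s = 1 | s = 0.75 | s = 0.5 | s = 0.25 |
|---|---|---|---|---|
| 30% vs 50% | 68% | 49% | 31% | 16% |
| 40% vs 60% | 66% | 45% | 27.5% | 14% |
| 50% vs 70% | 68% | 43% | 25% | 13% |

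The table shows the direction and how sensitivity would fall. It does not estimate what will happen in this trial.

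**The case against.** The strongest reply is that a governing definition already exists. 7.B3 defines an SAE for the whole study and 7.C applies it. An event is first an AE and is then tested for seriousness, so reporting an admission as an adverse event is compatible with it also being an SAE. 7.C even has SAEs notified on the Adverse Events Form. This stands, and it means 4.O3 does not flatly contradict 7.B3.

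A reader might infer four stronger things that the documents do not support:

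- *That infections are serious only with hypotension, acidosis, tissue necrosis or opportunism.* The protocol does not say only; it gives sufficient triggers. 7.D4 makes a wound infection treated with intravenous antibiotics an SAE with none of those features. The paragraph also looks damaged: an isolated word, *completed*, stands just before the first trigger, so it is unsafe to read the list as exhaustive.
- *That the named steroid effects have no severe grade.* 7.B2 grades all AEs from 1 to 5, and 7.D need not restate each grade. Several SAE steps in 7.D would plausibly meet 7.B3 on other criteria.
- *That about 22 infants per arm would change class* (0.32 × 70 = 22.4, from the cholangitis rate in Table 2). That rate is from one uncontrolled, treated series listed with N = 14, and no count out of 14 gives 32% (4/14 = 29%, 5/14 = 36%). Admission in every case, and the same rate on placebo, would also be assumptions.
- *That one arm is favoured.* Blinding argues against this.

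It is also fair that a misclassified infection does not disappear. 4.O3 still calls for a form within 24 hours, 4.H records hospital admissions, the DSMB reviews all AEs, and the stopping ground in 5.A.4 refers to adverse events, not to SAEs alone.

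What the reply does not remove is that no section says 7.B3 overrides the lists. 4.O3 names a distinct serious-event form with narrower triggers, and 7.D4 spells out readmission where 4.O3, 7.D5 and 7.D6 do not, which invites the narrow reading.

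**Conclusion.** The point holds as an unreconciled instruction. 4.O3 and Table 8 name SAE triggers narrower than 7.B3 and omit hospitalization; 7.D2, 7.D3, 7.D5 and 7.D6 use SAE as a severity step. Sites that follow them literally could record hospitalized events as non-serious.

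The consequence is lower SAE counts that vary between sites, and so lost sensitivity in the between-arm SAE comparison and in the DSMB's serious/non-serious summaries. It is not bias toward one arm, provided blinding holds. The size cannot be derived from the documents: it depends on the share of hospitalized events under-classified and on the true SAE risks, neither of which is given. The textual finding does not depend on the illustrative power figures. The change is worth making because it is cheap and improves safety reporting.

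**What to change.** - State in 4.O3, Table 8 and 7.D that the 7.B3 criteria, including hospitalization, decide seriousness for every event, and that the listed triggers are additional examples. Repair the septicemia paragraph of 4.O3 at the same time.
- Record the 7.B2 grade (1 to 5) separately from seriousness for each event, so that SAE no longer serves as a rung above moderate in 7.D.
- Have the DCC check the SAE flag against the hospitalizations already recorded under 4.H, and query mismatches.

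**Cost.** Protocol wording and a routine data check. Sites that had followed 4.O3 or 7.D literally would file more expedited reports.

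**Dependency.** SAE status is also tied to stopping study drug, in differing terms. 4.K3 refers to a serious adverse event as outlined in Section 7; 4.F3 refers to an SAE that the site PI thinks possibly related; 7.D4 refers to any SAE. Clarifying seriousness alone could change how many infants fall under 4.K3 as worded. These passages contradict each other and must be reconciled in the same amendment. No clinical rule is proposed here.

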5. STATISTICAL ANALYSIS AND DATA MANAGEMENT

5.A. Sample Size

5.A.1. Primary Endpoint

The primary endpoint (Hypothesis 1a) of this clinical trial is whether or not the subject has a serum total bilirubin <1.5 mg/dL with his/her native liver at 6 months after portoenterostomy. To determine the sample size for the clinical trial, we conducted a retrospective study of the level of serum total bilirubin and transplant-free survival in children with biliary atresia treated with portoenterostomy at the 14 ChiLDREN pediatric liver care centers. From the study, 54 of 118 infants (46%) had good bile drainage at 6 months, as determined by a serum total bilirubin level <1 mg/dL. (The results were tabulated at both 1 mg/dL and 2 mg/dL and the results were similar.) Our goal in this trial will be to improve the rate of good bile drainage at 6 months post-surgery from 50% to

75%. Using East-2000® (Cytel Software Company, Cambridge), a total of 110 subjects would need to be randomized to the two treatment groups in order to have 80% power to identify this difference at a 2-tailed 5% level of significance. To allow interim looks at the data after 50% and 75% of the subjects complete the trial using the O'Brien-Fleming spending function, the number of subjects that would be necessary is 114. To compensate for up to 20% attrition; we increased the sample size to a total of 140 subjects; e.g., 70 per group. Attrition will be defined as withdrawal by parents or guardians (which includes subjects who are lost to follow up) occurring within the first 6 months following portoenterostomy (prior to the time of evaluation of the primary outcome measure); however, data from all randomized subjects will be included in an intent-to-treat analysis.

5.A2. Secondary Endpoints

Hypothesis 1b is that improved bile drainage, as determined by serum total bilirubin with native liver, will be improved in the infants treated with corticosteroids compared to those treated with placebo. Serum total bilirubin concentrations are measured at each clinical visit, including 3 and 6 months after portoenterostomy, and at 12, 18 and 24 months of age. (The time point of 6 months after portoenterostomy is the primary endpoint). A serum total bilirubin value >1.5 mg/dL, transplant or death, is indicative of failure of the portoenterostomy. The time to the first value >1.5 mg/dL (when the value is initially >1.5 and then declines to ≤ 1.5 , the time to the first value >1.5 mg/dL after the decline will be used), to transplant or to death will be considered time to failure of the procedure. The two groups will then be compared by a Cox regression model fitted to the time to failure. Since the test of the primary endpoint is a special case of this analysis, there is greater power for this comparison than for the primary endpoint.

Hypothesis 2 is that survival with native liver at 24 months of age is improved in infants treated with corticosteroids compared to those treated with placebo. In the 118 subjects in our survey of the ChiLDREN centers, 60 (51%) were transplanted by 24 months of age. Similar to the primary endpoint, we will have 80% power to show a 50% improvement in this measure (lowering the transplant rate from 50% to 25%).

Hypothesis 3 is that growth will be improved in infants treated with corticosteroids compared to those treated with placebo. These secondary endpoints, weight for age Z-score (in subjects without ascites) and height for age Z-score, are continuous. Children at the time of portoenterostomy are expected to have normal or near normal growth (mean Z-score near zero). Changes in weight and height Z-scores will be compared between treatment groups. For these endpoints there will be 80% power to identify a difference of 0.55 standard deviations (SD) between groups when 110 subjects are randomized. Since a mean Z-score of -1.0 or less would represent impaired growth and a mean > -0.5 would represent satisfactory growth, there will be almost 80% power to differentiate between these two outcomes.

We do not have data to present power calculations for the other secondary endpoints (sufficiency of fat-soluble vitamins and incidence of ascites). We do not anticipate sufficient deaths by age 2 to compare survival between treatment groups.

5.A.3. Tertiary Endpoints

Tertiary endpoints are those that may be affected by improved liver function. The hypothesis is that infants treated with corticosteroids will have improved liver function at 12 and 24 months of age, which will result in lower INR, higher serum albumin, lower PELD score, higher platelet count, higher serum sodium concentration, lower serum bile acid concentration, lower PIVKA-II, higher mid-arm circumference and triceps skinfold thickness, better HRQOL, improved neurodevelopmental outcome, and adequate immunologic response to childhood immunizations. However, the study is not powered to detect differences in these variables. Therefore, analyses of these data will serve to generate specific hypothesis for future studies.

5.A.4. Interim Analysis

There are both short-term (e.g., bilirubin at 6 months post-portoenterostomy) and long-term outcomes (e.g., survival with a native liver and developmental assessments at 12 and 24 months of age). Although there is a relationship between bilirubin at 6 months and survival with a native liver, the intervention may impact these endpoints differentially and, especially, may impact development and growth in a manner independent of the level of bilirubin at 6 months. Therefore, the Steering Committee recommends that the trial should not be terminated early based on a test for either efficacy or futility. The Steering Committee recognizes that the DSMB will monitor adverse events and may recommend ending the study early if there is a significant imbalance in adverse events (risk to the participants) between the two treatment arms.

5.B. Data Analysis

General

Prior to unmasking the study and the start of any formal analyses, the data for each variable will be examined to identify unusual values that need to be queried, patterns of missing values and whether their distributions are non-Gaussian (i.e., have significant skewness and kurtosis). These analyses are, in general, performed conditional on one or more covariates known to affect the variable being studied; for example, values may be examined conditioned on age of the infant or age at time of portoenterostomy. Data from variables with non-Gaussian distributions will be transformed, if necessary, before building statistical models. Missing data patterns will be examined and, when necessary for the data analysis, missing data may be imputed by appropriate methods depending on the pattern and mechanism of the missing data. Baseline variables will be compared between groups. If a baseline variable is identified as significantly different between groups and it may affect the outcome measure, the analysis of the outcome measure will be repeated with this baseline variable included as a covariate. All models will include clinical site as a random effect.

Aim 1: To determine whether corticosteroid therapy decreases serum bilirubin concentration after portoenterostomy.

Hypothesis 1a: The probability of an infant having good bile drainage at 6 month after portoenterostomy (as defined by a serum total bilirubin level <1.5 ml/dL) will be greater in subjects treated with corticosteroids than in those treated with placebo.

This is the primary hypothesis of this study, upon which the sample size was calculated. A generalized linear model (e.g., a logistic regression model) with random effects will be used to test this hypothesis. The dependent variable is dichotomous: whether the infant has good bile drainage or not; transplantation or death is considered a failure in all analyses. The covariates that will be included in the model are the treatment group, baseline total bilirubin level, age of the infant at portoenterostomy, complications before the surgery, gender and race of the infant, presence of major congenital anomalies, as well as site as a random effect. The test of the primary hypothesis is a test of whether the coefficient of treatment group is zero.

Hypothesis 1b: Improved bile drainage (as defined by a serum total bilirubin level <1.5 mg/dL) will remain for a longer period in infants treated with corticosteroids than in those treated with placebo.

Using the same definition of good bile drainage as in the primary hypothesis, the duration of time with good bile drainage (time to onset of poor bile drainage, transplant or death, whichever comes first) will be modeled by Cox proportional hazards model using the same model as above. If there is a statistically significant difference, the profiles of the bilirubin for the two treatment groups will be compared and 95% confidence limits will be computed.

Aim 2: To determine whether corticosteroid treatment after portoenterostomy will improve outcome as defined by survival without transplantation at 24 months of age.

Hypothesis 2: Survival without liver transplantation will be greater at 24 months of age in infants treated with corticosteroids than in those treated with placebo.

A Cox proportional hazards model will be fitted to the time to transplant or death. The same covariates will be included in the model as for the previous hypothesis.

Aim 3: To determine whether corticosteroid treatment after portoenterostomy will improve growth of infants with biliary atresia.

Hypothesis 3: Weight and height Z-scores at 12 and 24 months of age will be higher in the infants treated with corticosteroids than in those treated with placebo.

The weight and height Z-scores at 12 and 24 months of age will each be modeled by a random effects model with the same covariates as above.

Aim 4: To determine whether corticosteroid treatment improves biochemical indicators of each of the fat-soluble vitamins after supplementation with standard doses.

Hypothesis 4a: Treatment with corticosteroids leads to improved bile drainage (hypothesis 1) which, in turn, increases the probability that an infant will achieve vitamin sufficiency of each of the fat-soluble vitamins following supplementation of AquADEK®.

Each vitamin will be analyzed separately. For hypothesis 4a, each subject will be classified as having achieved or not achieved vitamin sufficiency, first with supplementation and then without supplementation. Vitamin sufficiency will be defined as having achieved the target concentration ranges specified in Section 4.N8. Although we can model the outcome as a function of treatment group, the underlying hypothesis is that the outcome is a function of bilirubin level. Therefore, we will model the outcome by logistic regression using bilirubin as a surrogate for bile drainage; bilirubin may be included in the model either as a continuous measure or as a dichotomy where <1.5 mg/dL is defined as good bile flow and ≥ 1.5 mg/dL as inadequate bile flow. Gender and race of the infant, presence of major congenital anomalies, as well as site as a random effect will be included as covariates.

Hypothesis 4b: Treatment with corticosteroids leads to improved bile drainage (hypothesis 1) which, in turn, reduces the dose required for supplementation and the length of time of supplementation for each of the fat-soluble vitamins.

As in hypothesis 4a, each vitamin will be analyzed separately. There are two components to this hypothesis. The first is the total amount of supplementation and the second is the length of supplementation. We will compute the total amount of supplementation up to 6 months of age as the first dependent variable and the time to achieving target concentrations without supplementation as the second dependent variable. The first variable (after transformation) will be analyzed by a random effects model with bilirubin as the independent variable and the same covariates as in hypothesis 4a. The second variable will be modeled by Cox regression with the same independent variable and covariates.

Aim 5: To determine whether corticosteroid treatment after portoenterostomy will decrease the incidence of persistent ascites or ascites that requires medical treatment.

Hypothesis 5: The incidence of ascites will be decreased at 12 and 24 months of age in infants treated with corticosteroids than in those treated with placebo.

Similar to hypothesis 2, a Cox proportional hazards model will be fitted to the time to diagnosis with ascites.

Other endpoints will be analyzed similarly depending on whether they are continuous, dichotomous or time-to-event.

5.C. Data Management

5.C1. Case Report Forms

The Biometrics and Outcomes Research Core in the Department of Biostatistics at the University of Michigan will serve as the data coordinating center (DCC) and is responsible for data management and analysis. The DCC maintains a password-protected website for the ChiLDREN study. All transmissions to and from the website are encrypted using SSL. In addition to providing access to the study database, the website contains the protocol, manual of operations for ChiLDREN, current versions of the case report forms that are used at the time of subject enrollment and at follow-up visits, and other information related to the study. The case report forms do not contain any personal subject identifiers, except dates, such as date of birth, which are necessary for research purposes. Either the DCC will provide the case report forms or the study coordinator will print blank case report forms from the website. An investigator and/or study coordinator can only view data in the study database from his/her clinical site.

The case report forms are completed and countersigned by the investigator or study coordinator at each study visit. On the case report forms, each subject is identified by a subject identification number that consists of two-digit site number and a five-digit identification number. The last digit of the number is a check digit that is used to identify errors in transcription of the identification number. No other personal identification (except dates) is included on case report forms that are submitted to the DCC.

The original case report forms should be securely maintained in locked file drawers at the clinical study sites. Clean completed copies of the case report forms are sent monthly to the DCC where they are entered into the study database using double entry (entry and verification). Other forms are entered by the coordinator directly into the study website; these forms are also sent monthly to the DCC and entered a second time for verification.

5.C2. Quality Assurance

The DCC Project Manager/Clinical Monitor and/or Data Manager will review data submitted to the DCC for accuracy and completeness. The DCC Data Manager and/or Project Manager/Clinical Monitor will transmit to the study coordinators at each site any queries generated by the DCC and address all questions and concerns regarding the study protocol and problems with data entry. Site visits by the Project Manager/Clinical Monitor will be made annually to review case report forms for this study and for the ChiLDREN prospective database study. During these visits the Project Manager/Clinical Monitor will review the regulatory file, check all informed consent documents, and review study procedures with the study coordinators. Interim site visits may be made to centers with low compliance or high error rates. Performance reports will be generated quarterly to investigators and study coordinators at each center, as well as to Data Safety Monitoring Board (DSMB).

5.C3. Training

The DCC has developed general and project-specific manuals of operations to assist investigators and study coordinators at each center in following the ChiLDREN-approved projects, clinical trial protocols, entering and transferring data, and collecting, processing and shipping samples. The Project Manager/Clinical Monitor will be responsible for training the study coordinators at each center about this study protocol, the completion of source documents, and the use of the web-based entry system. The Project Manager/Clinical Monitor will also review with the central research pharmacist the proper procedures for shipping samples to the site research pharmacies. Similar training sessions of study coordinators have been held for two ChiLDREN retrospective studies and for the ChiLDREN prospective database study during face-to-face meetings, which were held in parallel with meetings of the ChiLDREN Steering Committee, as well as through conference calls. Test runs of data entry into the web-based data entry system will occur prior to site initiation. The Project Manager/Clinical Monitor will review the study protocol and data entry system, and check all regulatory documents prior to site initiation. In-service training for all study coordinators will be held quarterly via conference calls to review frequently encountered questions regarding the protocol, data entry, or sample processing.

